## PRÉCIS

## **Background:**

- Chronic Graft versus Host Disease (cGVHD) is a major late complication of allogeneic hematopoietic stem cell transplantation.
- The oral cavity is the second most commonly affected area in cGVHD and is a major cause of morbidity.
- Clobetasol is a high-potency topical corticosteroid widely used for a variety of inflammatory disorders of the skin and oral mucosa.
- Treatment of oral cGVHD by topical agents is an attractive strategy to potentially avoid adverse effects associated with systemic immunosuppression.

## **Objective:**

• To investigate efficacy of topical clobetasol 0.05% oral rinse for oral chronic graftversus-host disease (cGVHD)

## **Eligibility:**

• Patients age 12-99 years with clinically significant oral cGVHD.

## Design:

- This is a randomized, double blind, placebo-controlled, pilot study of clobetasol 0.05% topical oral rinse with an open label extension period.
- Patients will rinse oral cavity with 10cc of clobetasol 0.05% or placebo oral rinse for 2 minutes 3 times a day.
- Treatment duration will be for 2 weeks in the randomized phase and 2-4 weeks in the open label phase.
- Up to 40 patients will be enrolled on this pilot trial until 34 evaluable patients are assessed.

## STATEMENT OF COMPLIANCE

The trial will be carried out in accordance with International Council for Harmonisation Good Clinical Practice (ICH GCP) and the following:

• United States (US) Code of Federal Regulations (CFR) applicable to clinical studies (45 CFR Part 46, 21 CFR Part 50, 21 CFR Part 56, 21 CFR Part 312, and/or 21 CFR Part 812)

National Institutes of Health (NIH)-funded investigators and clinical trial site staff who are responsible for the conduct, management, or oversight of NIH-funded clinical trials have completed Human Subjects Protection and ICH GCP Training.

The protocol, informed consent form(s), recruitment materials, and all participant materials will be submitted to the Institutional Review Board (IRB) for review and approval. Approval of both the protocol and the consent form must be obtained before any participant is enrolled. Any amendment to the protocol will require review and approval by the IRB before the changes are implemented to the study. In addition, all changes to the consent form will be IRB-approved; an IRB determination will be made regarding whether a new consent needs to be obtained from participants who provided consent, using a previously approved consent form.

## **1 INTRODUCTION**

## **1.1 STUDY OBJECTIVES**

## 1.1.1 Primary Objective

To investigate efficacy of topical clobetasol 0.05% oral rinse for oral chronic graft-versus-hostdisease (cGVHD) during a four-week treatment period as assessed by Oral Mucositis Rating Scale (OMRS).

## 1.1.2 Secondary Objectives

- 1.1.2.1 To assess the effect of topical clobetasol on oral cGVHD related pain, sensitivity, and dryness.
- 1.1.2.2 To evaluate the basic pharmacodynamics and pharmacokinetics of clobetasol mouth rinse in cGVHD patients.
- 1.1.2.3 To obtain a pilot assessment of patient perceived oral health in cGHVD and its response to treatment with topical clobetasol.
- 1.1.2.4 To evaluate the validity of the NIH Oral cGVHD Clinical Scoring instrument.
- 1.1.2.5 To evaluate the immunological profile present at baseline and after clobetasol treatment in oral tissue to identify potential biomarkers for disease response or resistance to clobetasol.
- 1.1.2.6 To evaluate blood and saliva to identify potential biomarkers for oral cGVHD disease activity and response to topical clobetasol.

## **1.2 BACKGROUND AND RATIONALE**

## 1.2.1 Chronic Graft-Versus-Host-Disease

Allogeneic hematopoietic stem cell transplantation (alloHSCT) has been used increasingly for malignant and non-malignant disorders . Graft-versus-host disease (GVHD) is a major complication and a leading cause of morbidity and mortality in recipients of alloHSCT. GVHD results from immunologic attack by the donor's immune cells on the recipient's tissues and organs. Incidence and severity of GVHD vary depending on degree of mismatch of major histocompatibility antigens of the donor and host, age of donor and recipient, source of stem cells, and type of preparative regimen. Development of non-myeloablative conditioning regimens has led to a decrease in early post-transplant mortality and an increase in chronic GVHD (cGVHD). Almost 70% of patients who survive more than 100 days after alloHSCT will develop cGVHD, with the majority manifesting in the first year. The undersupply of related donors led to expanded use of unrelated and partially matched unrelated donors. Use of non-myeloablative conditioning regimens is related to more frequent use of both older donors and recipients. Taken together, these factors have increased the incidence of cGVHD.

Chronic GVHD has many similar features of autoimmune diseases, such as lupus, lichen planus, and scleroderma, and can have a varied clinical presentation. Mononuclear cellular infiltrates are found in many areas of the graft recipient, including the liver, skin, oral mucosa, and salivary glands. Recent NIH consensus conferences proposed new criteria for staging of cGVHD that consider extent of the disease, number of involved organs, and severity of functional impairment. Some of these criteria have been validated, and others require validation in future trials. Chronic GVHD can persist for months to years and requires long-term multidisciplinary management.

## 1.2.2 Oral involvement in cGVHD

Oral cGVHD is a common, major cause of morbidity and decrease in health-related quality of life (HRQOL) in long-term alloHSCT survivors. In a recent randomized trial of peripheral blood stem cell (PBSC) vs. bone marrow stem cells (BMSC) transplants, oral mucosal changes were the most common manifestation of cGVHD in BMSC recipients and the second most common (after skin) in PBSC transplants. Overall incidence in cGVHD was around 85%. Oral manifestations of cGVHD include lichen planus-like changes, mucosal atrophy and ulcerations, taste disturbances, and salivary gland hypofunction. Oral pain and food sensitivity are common, and not limited to patients with ulcerations. Oral discomfort was shown to be associated with decrease in food intake and weight loss in this group of patients. Recently, the contribution of oral cGVHD to inferior health-related QOL was reported . There have been several reports of increased incidence of oral squamous cell carcinoma (SCCA) after allo-HSCT, with history of oral cGVHD identified as an independent risk factor.

## 1.2.3 cGVHD Therapy

## 1.2.3.1 Systemic and topical corticosteroids

The treatment for cGVHD consists of various systemic immunosuppressive agents, most commonly systemic corticosteroids, cyclosporine, tacrolimus, mycophenolate, sirolimus and phototherapy. Long-term immunosuppressive treatment for GVHD has a variety of serious complications including life-threatening infections, aseptic bone necrosis, hypertension, and secondary diabetes.

Corticosteroids are the most commonly used systemic treatment of both acute and chronic GVHD. Immunosuppressive and anti-inflammatory effects of corticosteroids are mediated through multiple mechanisms including immune cell apoptosis and interference with dendritic cell maturation. The critical role of dendritic cells in the development of GVHD has been outlined in several studies. One study demonstrated the potential of GVHD prevention via depletion of host antigen presenting cells in a murine model.. In another animal study, local depletion of Langerhans cells in skin prevented GVHD. Corticosteroids have been shown to prevent development of dermal dendritic cells *in vitro*.. Additionally, topical corticosteroids induced apoptosis in the murine epidermal Langerhans cells and CD8+T cells.

Topical corticosteroids such as dexamethasone 0.01% oral rinse and clobetasol 0.05% ointment are used widely for treatment of oral cGVHD, although their efficacy has not been formally evaluated in this condition. Ointments and creams have a disadvantage of uneven and cumbersome application, furthermore, it is difficult to estimate the systemic versus local effect. Unlike solutions used as rinses, ointments can be easily swallowed and absorbed through the gastrointestinal tract. At the NIH Clinical Center, both dexamethasone oral rinse and clobetasol ointment have been used with variable success. In general, complicated application procedures reduce compliance and make evaluation of response difficult. Oral rinses have a particular advantage when a significant oral cavity area is affected as the contact with the entire surface is ensured with potential decrease in systemic absorption.

## 1.2.3.2 Clobetasol

Clobetasol is a readily available corticosteroid used topically in a wide variety of inflammatory conditions. Clobetasol 0.05% ointment is FDA approved for the treatment of inflammatory skin diseases and clobetasol spray is approved for psoriasis. Clobetasol ointment is widely used topically by oral medicine practitioners for the treatment of oral ulcerative conditions including oral lichen planus, a condition clinically and pathologically similar to oral cGVHD and has been shown to be safe and effective. When used 2 times a day for 4-8 weeks, the response rates exceeded 90%. There are few side effects associated with oral topical corticosteroid use with the most common being oral candidiasis. To reduce incidence of oral candidiasis infection, patients will be asked to swish and spit once per day with nystatin (100,000u/ml) rinse, which is a standard preventative measure in high-risk patients. Although there have been reports of adrenal suppression associated with high potency topical steroids, these were generally rare and occurred primarily in young children and in patients with large surface areas of involvement (skin). In one study, no changes in morning cortisol levels were observed when clobetasol was applied topically in the oral cavity for 2 months for oral lichen planus. However, other reports have indicated signs and symptoms of adrenal suppression in patients with severe erosion of the oral mucosa, as in erosive oral lichen planus, and long term use (years) of topical clobetasol. The effect of clobetasol and other steroids applied topically in the oral cavity on the ability of adrenal glands to respond to stress levels of ACTH has not been formally evaluated in cGVHD or in normal patients.

## 1.2.4 Trial Plan

Treatment of oral GVHD by topical agents is an appealing strategy because it would potentially avoid the adverse effects associated with systemic immunosuppression and reduce systemic exposure to glucocorticoids. Most importantly, using immunosuppressive agents locally would concentrate the treatment effects for potential maximum benefit. Conversely, use of systemic

agents for the same purpose would interfere not only with the undesirable GVH response, but also with immune responses directed against the malignancy (the graft vs. tumor effect), which is the principal mechanism through which reduced intensity transplants achieve sustained disease remission.

Therefore, we propose this pilot randomized double blind placebo controlled trial of topical clobetasol 0.05% oral rinse for oral cGVHD. Consenting subjects with clinically significant oral cGVHD will be randomized to receive clobetasol or placebo oral rinse for 2 weeks. All subjects will be evaluated biweekly. Clinically significant oral cGVHD is defined as a score of 20 or greater on the Oral Mucositis Rating Scale (OMRS) based on the patient cohort (over 250) seen in the NIH natural history of cGVHD protocol. At the first 2 week appointment, patients will be unblinded and subjects randomized to placebo will be assigned to additional 2-4 week open label treatment period with topical clobetasol rinse. All patients will therefore complete 4 weeks of treatment with the study drug (2 additional weeks for patients originally assigned to clobetasol arm and 4 weeks for patients assigned to placebo arm). All patients will be reevaluated 1 month following the open label period to evaluate the response and collect follow-up data.

Patients with progressive disease while on the clobetasol treatment as determined at any scheduled evaluation visit will be considered non-responders for the primary endpoint evaluation and will be taken off-study. Within 90 days of the end of the open label treatment period, all patients with evidence of benefit (response or stable disease) will be given an option to continue treatment with clobetasol 0.05% with or without additional treatment as deemed clinically necessary, up to one month. The proportion of responders in the active and placebo arm will be used as the primary outcome variable. As no standard definition of oral cGVHD response exists, for purposes of this pilot study, response will be defined as decrease of 25% or more on the OMRS (**Appendix A**). Difference in OMRS scores between the groups at the end of the 2 week blinded period and the change in OMRS score between beginning and the end of the 4 week treatment period with clobetasol oral rinse will serve as a secondary outcome variables. The study schedule of events is outlined in **Appendix E**.

The placebo design is justified by the following: a) there is no proven standard topical therapy for oral cGVHD, b) patients will be unblinded after 2 weeks of treatment (defined in Section **3.2.4**) and those on placebo will be allowed to cross over to the alternate treatment arm. This will allow all participants to receive the study drug for 4 weeks.

In addition to potential direct benefit to the cGVHD patients, this study is likely to provide valuable insights into the cellular and molecular alterations associated with the development of cGVHD and treatment with topical corticosteroids. This will lead to better understanding of the pathogenesis of cGVHD needed as the foundation for development of new therapeutic interventions.

## 2 ELIGIBILITY ASSESSMENT AND ENROLLMENT

## 2.1 ELIGIBILITY CRITERIA

## 2.1.1 Inclusion Criteria

- 2.1.1.1 Age: 12 years 99 years.
- 2.1.1.2 Diagnosis: clinically significant oral cGVHD after allogeneic HSCT with severity score of at least 2 on erythema subset and/or at least 1 on ulceration subset and a composite

score  $\geq$ 20 of the Oral Mucositis Rating Scale (OMRS) scale (**Appendix A**) confirmed by the principal investigator (PI), clinical study chair (CSC), or lead associate investigator (LAI).

- 2.1.1.3 Hematologic Function: Patients must have a platelet count  $\geq 20,000/\mu L$  at the time of the initial evaluation.
- 2.1.1.4 Informed Consent: All patients or their legal representative (for patients <18 years old) must sign an IRB approved informed consent document (cGVHD natural history protocol 04-C-0281 or any NCI protocol allowing for screening procedures) prior to performing studies to determine patient eligibility. After confirmation of patient eligibility all patients or their legal representative must sign the protocol specific informed consent. For pediatric patients age appropriate assent will be obtained in accordance with NIH guidelines.
- 2.1.1.5 Patients must be able to rinse and expectorate study medication rather than swallow it. Female patients must be willing to practice birth control (including abstinence) during and for two months after treatment, if of childbearing potential.
- 2.1.1.6 Patients must have the ability and willingness to come to Clinical Center for bi-weekly follow-up appointments.
- 2.1.1.7 No change in systemic immunosuppressive therapy (type or intensity level) within 2 weeks prior to enrollment.
- 2.1.1.8 A 7-day washout period is required if patients are currently using another oral topical treatment for mouth lesions. Patients currently using clobetasol oral topical treatment are not eligible for this study.

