#### 2.1.2 Exclusion Criteria

- 2.1.2.1 Documented hypersensitivity to clobetasol.
- 2.1.2.2 Use of clobetasol ointment intra-orally at any time during the last 6 weeks period.
- 2.1.2.3 Pregnant or breast-feeding females due to possible toxicity to the fetus or infant.
- 2.1.2.4 Inability to understand the investigational nature of the study to provide informed consent.
- 2.1.2.5 Patients who, for medical or other reasons, are unable to comply with the study procedures.

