## **3** STUDY IMPLEMENTATION

## 3.1 STUDY DESIGN

This is a randomized, double blind, placebo-controlled, pilot study of clobetasol 0.05% topical oral rinse with an open label cross-over or extension period. Consenting subjects with clinically significant oral chronic GVHD will be randomized to clobetasol 0.05% or placebo oral rinse. The placebo will be flavored with quinine, to approximate the "bitter" taste of clobetasol.

Subjects will be evaluated at bi-weekly intervals while on the study intervention. OMRS score will serve as the primary outcome measure. At the first 2 week interim appointment patients will be unblinded and started on the clobetasol oral rinse open label. In the absence of progressive oral disease on the scheduled interim evaluations during the 4-week clobetasol treatment period, all patients will complete a total of 4 weeks of treatment with clobetasol. Therefore, patients who were originally assigned to clobetasol arm will receive additional 2 weeks of treatment, and patients assigned to placebo arm will undergo an additional 4 weeks of treatment with clobetasol after unblinding. Patients with progressive disease after 2 weeks of therapy with clobetasol will be considered non-responders, taken off-treatment and treated as appropriate in consultation with primary clinician. Within 90 days of the end of the 1 month of treatment, all patients with evidence of benefit (response or stable disease) will be given an option to continue treatment with clobetasol 0.05% with or without additional treatment as deemed clinically necessary for 1 month after the conclusion of the initial treatment period. Additional follow-up appointment will be scheduled for all patients 1 month after completion of treatment. The change in OMRS scores from baseline to 4 weeks of mouth rinse usage will be the primary outcome variable. For the placebo group, the OMRS score at the end of the blinded phase/beginning of clobetasol rinse use (day 14) will serve as the baseline for the primary outcome. Difference in OMRS score between the groups (placebo and clobetasol) at the end of the 14-day blinded phase will serve as a secondary outcome measure. The study schedule of events is outlined in Appendix G.

# 

#	Because of problems with your teeth, denture or mouth have you	Never (0)	Hardly ever (1)	Occasionally (2)	Often (3)	Very Often (4)
1	Had trouble pronouncing words					
2	Felt sense of taste has worsened					
3	Had painful aching in the mouth					

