## 3.2.2 Duration of Drug Therapy

Patients will be treated with study medication for up to 4 weeks initially. If patients enter the continuation treatment period, they can be treated for up to an additional 4 weeks. Patients may be allowed to enter the continuation treatment period up to 90 days after the last day of treatment.

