## **Appendix C**)

- 6. Oral Global Scale (Appendix D)
- 7. Painometer (POM) Assessment (Appendix E)
- 8. Oral Health Impact Profile- OHIP-14 (Appendix F)
- 9. Hematology: Complete blood counts, with differential and platelet count. Within 72 hours prior to initial evaluation.
- 10. Chemistries: Electrolytes (including sodium, potassium, chloride, CO2, calcium, phosphorus and magnesium), creatinine, BUN, glucose, SGOT, alkaline phosphatase, SGPT, bilirubin, PT/INR and PTT, serum cortisol level and TBNK panel. Within 72 hours prior to initial evaluation.
- 11. FSH, LH, TSH, T4, CMV by PCR, and HSV by PCR.
- 12. Urine or Serum Pregnancy test: For all females of childbearing potential. This test is to be performed within 7 days prior to enrollment on the trial.
- 13. Urine glucose Within 72 hours prior to initial evaluation.
- 14. Biopsy of buccal mucosa (4 mm punch) on patient's right side OR of buccal area with GVHD involvement for histopathological examination.
- 15. Research blood sample collection (18cc)
- 16. Five minute saliva sample, with and without paraffin stimulation
- 17. Short ACTH stimulation test, within 1 week prior to initial evaluation.
- 18. Clinical oral photo series
- 19. Adrenocorticotropic Hormone blood level within 1 week prior to initial evaluation.
- 20. Hemoglobin A1C level

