## 15.7 APPENDIX G: SCHEDULE OF EVALUATIONS AND EVENTS

Patients Randomized to Clobetasol Oral Rinse Schedule:

Patient Evaluations and Events	Screening and Baseline (Day -7 to 0 )*	Day 0 *	Interim Evaluation (Day 14) *g	End of Intervention (Day 28)*	Follow-up (Day 56) * (or end of treatment visit)	Follow up (3 months and 6 months post treatment) #
History and Physical Exam t	Xt		Xt	Xt	Xt	Xt
NIH Advanced Directives Form						
cGVHD NIH Organ Staging	X				X	
Clinical Photographs	X		X	X	X	
Urine pregnancy test	X					
Informed Consent	X					
Randomization	X					
CBC, Acute care, mineral and liver panel & LDH, TBNK	X		X	X	X	
Serum Cortisol Level	X		X	X	X	
Research Saliva and Plasma Collection	X		X	X	X	
OMRS	X		X	X	X	
Oral cGVHD Clinical Scoring	X		X	X	X	

Patient Evaluations and Events	Screening and Baseline (Day -7 to 0 )*	Day 0 *	Interim Evaluation (Day 14) *g	End of Intervention (Day 28)*	Follow-up (Day 56) * (or end of treatment visit)	Follow up (3 months and 6 months post treatment) #
Oral HSV by PCR	Х			X		
Oral Pain, Sensitivity, Dryness Scales	Х		X	X	X	
Global Scale			X	X	X	
РОМ	Х		X	X	X	
OHIP-14 (Oral QOL)	Х		X	X	X	
Biopsy/Tissue Collection	Х			Xt		
ACTH Stimulation Test	Х			X	X p	
Adrenocorticotropic Hormone blood level	Х			X	Х	
Hemoglobin A1C level	Х	Х	X	X	X	
Compliance Evaluation			X	X		
Monitoring for Adverse Events			X	X	X	X
Start of intervention		Х				
Completion of the intervention				X		

 $^{*}\pm 2 \ days$ 

tOptional

p Per PI discretion (at day 56 or day 70 visit depending on subject randomization group) if there is concern for endocrine side-effects)

# This follow up can be done in person or via telephone call as per Section **3.7**g Patients initially randomized to 2 weeks of placebo will have two Day 14 Interim Evaluation visits, one at unblinding and one after 14 days of clobetasol therapy.

h As indicated in Section 11.5, all subjects  $\geq$  age 18 will be offered the opportunity to complete an NIH advanced directives form. This should be done preferably at baseline but can be done at any time during the study as long as the capacity to do so is retained. The completion of the form is strongly recommended, but is not required.

Version Date: January 24, 2017

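### A continuation course may start after the birth-control commitment has ended, and no repeat pregnancy test is required before it

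*Combined protocol and SAP*

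**What the plan says.** **Contraception.** Section 2.1.1.5: "Female patients must be willing to practice birth control (including abstinence) during and for two months after treatment, if of childbearing potential". Section 11.4.4 adds a general expectation that women who can conceive use effective birth control. It gives no duration and no test.

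**Restart.** Section 3.2.2: "Patients may be allowed to enter the continuation treatment period up to 90 days after the last day of treatment". On length, the same section says: "If patients enter the continuation treatment period, they can be treated for up to an additional 4 weeks". Section 1.2.4 opens the offer with "Within 90 days of the end of the open label treatment period, all patients with evidence of benefit", and Section 3.1 with "Within 90 days of the end of the 1 month of treatment, all patients with evidence of benefit". In both, benefit means response or stable disease.

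**Pregnancy testing.** Section 3.3.1, item 12, requires a urine or serum test in all females of childbearing potential: "This test is to be performed within 7 days prior to enrollment on the trial". In Appendix G the row "Urine pregnancy test" is marked only under screening and baseline. The interim, end-of-treatment and follow-up lists (Sections 3.3.2 to 3.3.4) contain no pregnancy test. No evaluation is specified for entry to continuation.

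**Exclusion.** Section 2.1.2.3: "Pregnant or breast-feeding females due to possible toxicity to the fetus or infant". It appears only as an enrollment criterion.

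**The concern.** Two timed rules do not fit together. One releases a patient from contraception two months after treatment. The other lets her take the drug again up to 90 days after treatment. The first course needs a recent negative test, while a second course after an off-drug gap needs none.

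The fetal risk is one the protocol itself names. It excludes pregnancy because of possible toxicity, notes birth defects in animals with strong corticosteroids (Section 11.4.4), and says that low levels of topical steroid are absorbed through the oral mucosa at an unknown rate (Section 11.4.1). A site that follows the text exactly could re-expose a pregnancy that exclusion 2.1.2.3 is meant to keep out. This is a patient-safety point only.

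**Working it through.** The documents give no figure of their own for this gap, so there is none to reproduce. The check is calendar arithmetic plus a search for anything that would close the gap.

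**1. Part of the window after the commitment ends**

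Inputs: latest restart at day 90 after the last dose (3.2.2); commitment of two months after treatment (2.1.1.5).

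Formula: uncovered days = 90 − length of two months in days.

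Every treatment end date from 2016 to 2019 was tried; two calendar months ran from 59 to 62 days.

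| Reading of two months | Days | Uncovered days | Share of window |
|---|---|---|---|
| Longest calendar case | 62 | 90 − 62 = 28 | 28/90 = 31% |
| Taken as 60 days | 60 | 90 − 60 = 30 | 30/90 = 33% |
| Shortest calendar case | 59 | 90 − 59 = 31 | 31/90 = 34% |
| Taken as 8 weeks | 56 | 90 − 56 = 34 | 34/90 = 38% |

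On calendar months, restarts from about day 60 to 63 through day 90 fall after the commitment has ended. Earlier restarts do not.

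**2. Age of the only test at the latest restart**

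This assumes that dosing starts at enrollment and the test was done 7 days before.

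- Clobetasol arm: 7 + 28 + 90 = 125 days.
- Placebo arm (14 days of placebo, then 28 of clobetasol): 7 + 42 + 90 = 139 days.

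**3. Potential exposure in one undetected case**

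Inputs: 3 rinses a day (3.2.1), 5 mg per 10 mL rinse (13.1), up to 4 weeks (3.2.2). This assumes a full course with no missed doses.

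- Rinses: 28 × 3 = 84.
- Daily amount: 3 × 5 = 15 mg.
- Course total: 84 × 5 = 420 mg.

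These amounts are rinsed and spat out; they are not an absorbed or fetal dose.

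**4. Whether another provision closes the gap**

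- The last scheduled in-person evaluation is 28 days after the open-label period (3.3.4). After that, contact is every 3 months and may be by telephone (3.7), so a restart at days 60 to 90 can fall between contacts.
- Pregnancy is not listed among the reasons to stop therapy (3.8.1) or leave the study (3.8.2). Investigator discretion could be used, but only if the pregnancy is known.
- Appendix G as visible has no column for the start of continuation.

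**The case against.** The strongest reply is that the gap is narrow. Continuation is itself treatment, so birth control is required from its first dose and no dosing day lies outside the commitment. Harm needs a chain of events: childbearing potential, contraception stopped after two months, conception in the following month, and a restart before day 90 with the pregnancy unrecognised. Section 11.4.4 can be read as a standing expectation on anyone who will take study drug. Section 3.1 describes continuation as lasting one month after the initial period, which taken literally falls inside the two months. Entry is discretionary, and Section 11.4.4 says ovarian failure is common after transplant. Finally, no repeat test is required at any later point, including before placebo patients first take clobetasol, so the day 60 to 90 window may look like a pretext for a general preference for more testing.

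Much of this limits the weight. The window share is a share of days, not of restarts, and the affected number may be zero. It does not close the gap. Renewed contraception at restart does not detect a conception that came before it. Section 11.4.4 has no duration and no test. Section 3.2.2 expressly permits the late start. Placebo patients crossing over at day 14 are still under the commitment, so the rules do not conflict there. The consent pages, which might say more, were not available; the point concerns the protocol text only.

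**Conclusion.** The concern holds. Read as written, the protocol allows clobetasol to be restarted 28 to 31 days beyond the end of the contraception commitment, with the only pregnancy test by then up to 125 or 139 days old. The exposure at issue is limited to a conception in the off-drug interval that is undetected at restart.

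Those affected would be patients of childbearing potential, with response or stable disease, who restart late, in a trial capped at 40. The documents give no count. The size of the gap rests on calendar months; an 8-week reading makes it 34 days. The change should be made because the harm could be irreversible and the remedy is cheap.

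**What to change.** - **Section 3.2.2 and Appendix G:** for patients of childbearing potential, require a negative urine or serum pregnancy test within 7 days before any continuation course, and re-apply exclusion 2.1.2.3 at that point. Add the matching schedule entry.
- **Section 2.1.1.5:** state that the commitment also covers any continuation course and the two months after its last dose.
- **Optional:** extend contraception through the whole 90-day window, or until continuation is declined. This would reduce the uncovered span to 0 days, but it burdens patients who never restart, so the test is the better core change.

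The cost is short wording changes in two sections, one schedule entry, and one repeat of a screening test for the few patients concerned. Without the optional step, patients who do not restart need no extra contraception.
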